- 1749 • Change between baseline and each efficacy outcome assessment visit in best-
 1750 corrected ETDRS visual acuity score (e.g., mean change from baseline in visual
 1751 acuity, distribution of change from baseline in visual acuity based on clinically
 1752 meaningful cut points of improvement or worsening of visual acuity).
- 1753 • Change in calculated retinal thickening as assessed by optical coherence
 1754 tomography.
- 1755 • Change in retinal thickness at the center of the macula as assessed by stereoscopic
 1756 color fundus photography.
- 1757 • Change in area of retinal thickening as assessed by stereoscopic color fundus
 1758 photography.

1759

1760 **6.7 Statistical Guidelines for Interim Monitoring by the DSMC**1761 **6.7.1 Interim Monitoring for Safety**

1762 The SCORE Study will use repeated confidence intervals to continuously monitor the
1763 safety indicator variables mentioned in section 6.5. Safety rates will be reported
1764 separately in the two disease areas, but injection arms will be pooled to increase
1765 accuracy of the estimates.

1766

1767 **6.7.2 Interim Monitoring for Efficacy**

1768 The primary efficacy outcome occurs at 12 months from the randomization visit. The
1769 recruitment pattern is unpredictable. Information concerning the primary outcome
1770 will accrue as participants complete their 12-month visit and thus "information time"
1771 is the percent of the 486 patients in each trial expected to have completed this visit.

1772

1773 Of the Type I error (α) = .05 for each trial, α = 0.005 will be allocated for
1774 interim monitoring and the remaining α = 0.045 will be reserved for the final
1775 analysis. With α = 0.045 for the final analysis, the estimate of the sample size
1776 does not need to be increased for interim monitoring. Interim testing will be carried
1777 out using the Lan-DeMets interim monitoring boundary with an O'Brien-Fleming-
1778 type spending function where at most 0.005 cumulative α can be spent prior to the
1779 final analysis. The "height of the hurdle" is highest when the information fraction is
1780 smallest and decreases as additional patients complete 12 months. The "height of the
1781 hurdle" can be calculated for each DSMC meeting based on the number of patients
1782 expected to have completed the 12-month visit and the α spent by previous
1783 "looks" by the DSMC. With the specification that the total α for interim

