1784 monitoring is 0.005, the maximum amount the DSMC can "spend" is 0.005. If the
1785 DSMC looks more often, it will "spend" less per look.

1786

1787 Formally, if t is the information fraction, $B(t)$ is the 2-sided cumulative O'Brien-
1788 Fleming-type spending function of Lan & DeMets with final value $B(1) = 0.005$, and
1789 $S(t)$ is the two-sided cumulative spending function used by SCORE, then

$$1790 S(t) = \begin{cases} B(t) & \text{for } 0 \leq t < 1 \\ 0.05 & \text{for } t = 1 \end{cases}$$

1791
1792 At each interim inspection, the three comparisons will be made using the Lan-DeMets
1793 methodology, and the results combined using Hochberg's sequentially rejective
1794 procedure as described in the MOPP, section 6.4.

1795 **6.7.3 Interim Monitoring for Futility**

1796 The DSMC will consider futility as well as safety and efficacy. One method of
1797 statistically assessing futility is to use conditional power to estimate the likelihood of
1798 statistical significance given the observed efficacy results and various possible
1799 choices for the remaining results.

1800

1801 **6.7.4 Analyses and Results Requested to be Considered Prior to** 1802 **Recommending Early Termination**

1803
1804 Before recommending early termination, the DSMC will consider:

- 1805 • internal consistency of primary and secondary results
- 1806 • internal consistency of primary and secondary results by subgroups
1807 defined by baseline characteristics (e.g. visual acuity categories, categories
1808 based on length of history of CRVO or BRVO, and time period of
1809 enrollment)
- 1810 • distribution of baseline prognostic factors among the three groups
1811 (standard care, 4 mg, 1 mg)
- 1812 • consistency of primary and secondary results across clinical centers and
1813 among centers enrolling larger numbers of patients

1814 • possible bias in assessment of primary and secondary response variables,
1815 particularly visual acuity, given the unmasked implementation of standard
1816 care versus intravitreal triamcinolone
1817 • possible impact of missing data from missed patient visits for assessment
1818 of the primary and secondary response variables
1819 • possible differences in concomitant interventions or medications.

1820 **6.7.5 Study Timeline and DSMC Data Reviews**

1821 The DSMC will meet to review study data starting in November 2004, and every 6
1822 months until 3-year follow-up is concluded on all study participants. Table 6 depicts

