1823 the fractions of the population enrolled, with 1 year follow-up, and with 3 year
1824 follow-up, assuming that enrollment is constant, starts in August 2004, and takes 18
1825 months. Under this assumption, there will be 10 DSMC meetings. Formal interim
1826 inspection for 1-year efficacy will take place only during the four meetings when the
1827 information fraction is nonzero, that is, in November and May of 2005 and 2006.

1828 **Table 6: Study Timeline for DSMC Data Reviews**

1829 Date of DSMC Meeting	1830 Fraction		
	1831 Enrolled	1832 With 1-year 1833 follow-up	1834 With 3-year 1835 follow-up
November 2004	2/9		
May 2005	5/9		
November 2005	8/9	2/9	
May 2006	1	5/9	
November 2006		8/9	
May 2007		1	
November 2007			2/9
May 2008			5/9
November 2008			8/9
May 2009			1

1832 7. Confidentiality and Access to Source Data / Documents

1833 The investigators will maintain the highest degree of confidentiality permitted for the clinical and
1834 research information obtained from participants in this clinical study. Medical and research
1835 records should be maintained in the strictest confidence. However, as part of the quality
1836 assurance and legal responsibilities of an investigator, the site must permit authorized
1837 representatives of the sponsor(s), the SCORE Coordinating Center, and regulatory agencies to
1838 examine (and when permitted or required by applicable law, to copy) clinical records for the
1839 purposes of quality assurance reviews, audits and evaluation of the study safety and progress.
1840 Unless required by the law, no copying of records with personally identifying information will be
1841 permitted. Only the coded identity associated with documents or other participant data may be
1842 copied (obscuring any personally identifying information) or transmitted to the SCORE
1843 Coordinating Center. Authorized representatives as noted above are bound to maintain the strict
1844 confidentiality of medical and research information that may be linked to identified individuals.
1845 The site will normally be notified in advance of monitoring and auditing visits.

1846

1847 8. Summary of Good Clinical Practice Compliance

1848 This trial will be conducted in accordance with Good Clinical Practice (GCP) using the guidance
1849 documents and practices offered by ICH and FDA, and in accordance with the Declarations of
1850 Helsinki and the policies and procedures for the SCORE Coordinating Center at The EMMES

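### Does the wrong date in Section 6.7.5's list of interim efficacy looks require a change to the monitoring plan?

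*Combined protocol and SAP*

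**What the plan says.** Section 6.7.5 has the DSMC review data from November 2004 and then every 6 "months until 3-year follow-up is concluded on all study participants". It gives a projection, "Table 6: Study Timeline for DSMC Data Reviews", of the fractions enrolled, with 1-year and with 3-year "follow-up, assuming that enrollment is constant, starts in August 2004, and takes 18" months. On that basis it counts 10 meetings, the last in May 2009. It then says that formal interim "inspection for 1-year efficacy will take place only during the four meetings when the" "information fraction is nonzero, that is, in November and May of 2005 and 2006".

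Section 6.7.2 holds the operative rule. Information time is the share of the 486 participants in each trial expected to have completed the 12-month visit. The section concedes that the "recruitment pattern is unpredictable", and says that the height of the boundary "can be calculated for each DSMC meeting based on the number of patients" expected to have reached that visit and on the alpha already spent. The function S(t) "is the two-sided cumulative spending function used by SCORE, then" set equal to an O'Brien-Fleming-type Lan-DeMets function B(t), with B(1) = 0.005, for t below 1, and to 0.05 at t = 1.

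The note in Section 4.8, for version 7.0 and higher (10 February 2008), closes enrolment on 29 February 2008 and follow-up on 28 February 2009. The Précis accordingly gives follow-up of 1 to 3 years.

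**The concern.** The sentence in Section 6.7.5 reads as a restriction: formal looks happen at these meetings and no others. Yet one of the four dates falls before any participant could have a 12-month outcome. The count of four also does not match the number of interim looks that Table 6 implies, because a meeting at t = 1 belongs to the final analysis.

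The section was also not revised for version 7.0. A trial that enrols until 29 February 2008 would still be accruing 12-month outcomes at meetings in 2007 and 2008, none of which is listed. In addition, some participants will stop before month 36, so 3-year follow-up cannot be concluded on everyone.

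If the list governed, two things would be in doubt: which looks were prespecified, and whether interim alpha was spent as planned. That would bear on the type I error of the primary comparisons.

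**Working it through.** **Inputs.** Constant enrolment over 18 months from August 2004 (Section 6.7.5); outcome at 12 months, S(t) and B(1) = 0.005 (Section 6.7.2); closing dates (Section 4.8).

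**1. Reproduce Table 6.** Count August 2004 as month 1 and take each meeting at the end of its month m. The 1-year fraction is t = (m − 12)/18, limited to the range 0 to 1. With z = 2.807 (two-sided 0.005), B(t) = 2[1 − Φ(2.807/√t)].

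| Meeting | m | (m − 12)/18 | Table 6 | Cumulative alpha |
|---|---|---|---|---|
| May 2005 | 10 | below 0, so 0 | blank | 0 |
| November 2005 | 16 | 4/18 = 2/9 | 2/9 | 2.6 × 10⁻⁹ |
| May 2006 | 22 | 10/18 = 5/9 | 5/9 | 0.00017 |
| November 2006 | 28 | 16/18 = 8/9 | 8/9 | 0.0029 |
| May 2007 | 34 | 22/18, capped at 1 | 1 | S(1) = 0.05 |

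The table is right for its own assumption. Counting to the start of the month instead gives 1/6, 1/2 and 5/6 for the three middle rows, but May 2005 is still 0 and May 2007 is still 1. So May 2005 is wrong under either convention, and the other three listed dates are right.

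**2. The count.** Four is the number of filled 1-year cells, and also the number of meetings held in 2005 and 2006. It is not the number of interim looks: those need 0 < t < 1, and there are three.

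**3. What the wrong date costs.** B(0) = 0, so a look in May 2005 spends nothing and has no outcome data to test. May 2007 is not on the list, which agrees with S(1) = 0.05.

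**4. Slower enrolment.** The documents give no actual accrual. As an illustration, assume constant enrolment from August 2004 to February 2008, which is 43 months. Then t = (m − 12)/43:

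- November 2005, May 2006, November 2006: 0.09, 0.23, 0.37
- May 2007, November 2007: 0.51, 0.65
- May 2008, November 2008: 0.79, 0.93

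That makes seven interim opportunities, four of them unlisted. Cumulative spending by November 2008 (m = 52, t = 40/43) would be 2[1 − Φ(2.807/√0.930)] = 2[1 − Φ(2.91)], about 0.0036, still under 0.005. The cap depends on t, not on the calendar or the number of looks.

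**5. The 3-year wording.** Month 36 by 28 February 2009 requires enrolment by 28 February 2006, or by about 25 April 2006 if the 8-week visit window is used in full. Later entrants cannot reach it, so the phrase in Section 6.7.5 cannot hold for a trial still enrolling after that. The meeting schedule itself still covers the study, since its last meeting, May 2009, falls after follow-up ends.

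**The case for a change.** The best argument for a change is that both conflicts sit in current text. Section 6.7.5 uses restrictive wording, names a date that its own table rules out, and omits meetings that would carry information if enrolment ran to its closing date. Monitoring plans should let an outside reader tell which looks were prespecified, and correcting a sentence costs nothing.

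Part of this stands. May 2005 should not be on the list, the word *four* should be three if interim looks are meant, and the phrase on 3-year follow-up disagrees with Section 4.8 and the Précis.

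The rest does not. The restriction attaches to the condition of nonzero information, which the sentence states before it gives any dates; the dates only illustrate that condition under a stated enrolment assumption. Table 6 is expressly conditional on 18 months of enrolment, so slower accrual makes it an outdated projection, not an error. A Lan-DeMets boundary does not need the number or dates of looks fixed in advance, and Section 6.7.2 uses it in that way. On follow-up, the Section 4.8 note says outright that the 3-year rule belonged to versions 6.0 and earlier, so nobody running the trial would be misled.

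**Conclusion.** This is a clerical mismatch between a sentence and the table beside it, together with one phrase that was not updated. No change to the plan follows. One of four listed dates is wrong; it carries t = 0 and zero alpha. The interim cap of 0.005, the 0.045 kept for the final analysis, the boundary calculation and the sample size are the same whichever dates are printed. All four dates precede version 7.0, so correcting them would alter no look still to come, and the rule needed for later meetings is already in Section 6.7.2.

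The conclusion rests on two readings: that the DSMC statistician follows the information-time rule of Section 6.7.2 where it differs from the illustrative dates, and that the Section 4.8 note governs the end of follow-up. Both are the natural readings of the text. The 43-month figures are an illustration under assumed constant accrual, and the conclusion does not depend on them.

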Appendix 1: Scheduled Study Evaluations

	Baseline	4-month interval follow-up visits									Safety ²	
		M4	M8	M12	M16	M20	M24	M28	M32	M36	D4	M1
Informed consent	X											
Urine pregnancy test	X ³											
Medical/ocular history	X ³											
Blood pressure	X ³			X			X			X		
Visual acuity	X ^{4,5}	X ⁵	X ⁵	X ⁵	X ⁵	X ⁵	X ⁵	X ⁵	X ⁵	X ⁵	X ⁷	X ⁷
Manifest refraction	X ⁵	X ⁵		X ⁵			X ⁵			X ⁵		
IOP	X ^{3,5}	X ⁵	X ⁵	X ⁵	X ⁵	X ⁵	X ⁵	X ⁵	X ⁵	X ⁵	X ⁷	X ⁷
Ophthalmic examination ⁸	X ^{3,5}	X ⁵	X ⁵	X ⁵	X ⁵	X ⁵	X ⁵	X ⁵	X ⁵	X ⁵	X ⁷	X ⁷
Lens assessment ⁹	X ^{3,5}	X ⁵		X ⁵			X ⁵			X ⁵		
Fundus photos												
Study Eye	M7F ³	M3F	M3F	M7F	M3F	M3F	M7F	M3F	M3F	M7F		
Non-study Eye	M3F ³			M3F			M3F			M3F		
FA	X ³	X		X			X					
OCT	X ^{5,10}	X ⁵	X ⁶	X ⁵	X ⁶	X ⁶	X ⁵	X ⁶	X ⁶	X ⁵		
Steroid injection /Laser ¹	X	X	X	X	X	X	X	X	X			

M= month

M7F= Modified 7-Field photos

Q= every

M3F= Modified 3-Field photos

D= day

¹ Retreatment with steroid injections or laser photocoagulation (if applicable) should be administered at 4-month intervals unless there are specific reasons not to treat in which case the investigator may decide to postpone treatment (see protocol section 4.8.3).

² Safety visits are performed at Day 4 and Month 1 after each injection.

³ To be performed within 21 days prior to randomization.

⁴ To be performed within 8 days prior to randomization

⁵ Examination data to be collected on both eyes.

⁶ Examination data to be collected on study eye only.

⁷ Examination data to be collected on the injected eye only.

⁸ Examination includes both a dilated fundus examination and a slit-lamp examination.

⁹ To be performed using the modified AREDS lens grading system.

¹⁰ OCT measurements will be performed twice on the same day in both eyes. This will occur within 21 days prior to randomization.

Note: Visit windows at M8, M16, M20, M28, M32 may be extended, if necessary, so that the visit occurs no sooner than 3.5 months from the last treatment.
